#### 9.4.2 Safety analyses

All safety analyses will be performed on the Safety Population.

The **observation period of safety data** is divided into 3 main segments:

- The pre-treatment period is defined as the time from informed consent up to the time of the first injection of IMP
- The whole on-treatment period is defined as the time from the first injection of IMP up to 30 days (7 days for hypoglycemia) after the last injection of IMP;
  - The 30-week core on-treatment period is defined as the time from the first injection of IMP up to Visit 10 (Week 30) (or Day 210 if Visit 10 [Week 30] visit is missing) or up to 30 days (7 days for hypoglycemia) after the last injection of IMP, whichever comes earlier
- The 30-week on-study period is defined from the first injection of IMP up to Week 30, irrespectively if IMP was still used or already discontinued at Week 30.
- The post-treatment period is defined as the time starting 31 days (8 days for hypoglycemia) after the last injection of IMP (after the whole on-treatment period)

The AE observations will be classified per the observation periods of safety data as defined above into:

- **Pre-treatment AEs** are AEs that developed or worsened or became serious during the pre-treatment period
- **Treatment-emergent AEs (TEAEs)** are AEs that developed or worsened or became serious during the on-treatment period
- **Post-treatment AEs** are AEs that developed or worsened or became serious during the post-treatment period.

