### **Intervention groups and duration:**

The study will comprise 4 periods:

- An up to 3-week Screening Period (with a minimum of 11 days)
- A 30-week double-blind, placebo-controlled Core Treatment Period, for efficacy and safety assessment
- A 26-week double-blind, placebo-controlled Treatment Extension Period; participants will remain on the randomized investigational medicinal product (IMP) regimen
- A 6-week Follow-up Period to collect post-treatment safety information for all participants after last dose of IMP

The maximum study duration per participant will be 65 weeks.

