### **Handling of participants after permanent intervention discontinuation**

Every effort should be made to maintain participants in the study. Participants will be followed-up according to the study procedures specified in this protocol up to the scheduled date of study completion, or up to recovery or stabilization of any AE to be followed-up as specified in this protocol, whichever comes last.

If possible, the participants will be assessed using the procedure normally planned for the EOT Visit including a PK sample when the permanent discontinuation occurred during the core treatment period and visit can be scheduled 7 days after the permanent discontinuation of intervention. For participants who discontinue IMP but remain in the study, the remaining visits should occur as scheduled where possible. The Investigators should discuss with them key visits to attend. All efforts should be made to continue to follow the participants for primary and secondary endpoints, after the discontinuation of treatment.

The value of all their study data collected during their continued involvement will be emphasized as important to the public health value of the study. Participants who withdraw from the study intervention should be explicitly asked about the contribution of possible AEs to their decision, and any AE information elicited must be documented.

All cases of permanent intervention discontinuation must be recorded by the Investigator in the appropriate pages of the e-CRF when considered as confirmed.

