**Table 6 - Safety analyses**

Endpoint	Statistical Analysis Methods
AEs	
All AEs will be coded to a "LLT", "PT", "HLT", and "HLGT" and associated "SOC" using the version of MedDRA currently in use by the Sponsor at the time of database lock.
 
Adverse event incidence tables will be presented by primary SOC (sorted by internationally agreed order), HLGT, HLT and PT (sorted in alphabetical order) for each treatment group, showing the number (n) and percentage (%) of participants experiencing an AE.
 
The primary focus of AE reporting will be on TEAEs. Pretreatment and posttreatment AEs will be described separately.
 
Adverse event incidence table will be provided by treatment group for all types of TEAEs: all TEAEs, all treatment-emergent SAEs, all TEAEs leading to permanent treatment discontinuation and all TEAEs leading to death.
 
Tables will be presented on the "30-week main on-treatment period" and on the "whole on-treatment period including the 26-week controlled Treatment Extension Period".

Endpoint	Statistical Analysis Methods
	Adverse events, SAEs and AEs leading to death tables also will be presented on the 30-week on-study period too.
Hypoglycemia	
The number (%) of participants with at least 1 hypoglycemia event during the whole on-treatment period will be assessed per type of hypoglycemic event (see Section 8.2.5) and according to time of occurrence (nocturnal [ie, 00:00 to 05:59 am], any time of the day). Documented hypoglycemia (symptomatic or asymptomatic) will be also evaluated for the more stringent SMPG threshold of <54 mg/dL (3.0 mmol/L).
 
Summaries will be presented overall and by type of event for each treatment group.
 
The total number of events (per 100 participant-years) will be computed and summarized overall and by type of event for each treatment group.
 
Similar summaries will also be provided for the 30-week core on-treatment period.

Vital signs and laboratory data	For quantitative safety parameters based on central laboratory/reading measurements, descriptive statistics will be used to summarize results and change from Baseline values by visit and treatment group.

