2.1.4 Safety endpoints

The safety analysis will be based on the reported adverse events (AE), hypoglycemia and other safety information, such as clinical laboratory data, vital signs, and ECG.

Observation period

The period related to treatment will be divided into 3 main segments:

- The **pre-treatment** period is defined as the time from informed consent up to the time of first injection of IMP.
- The whole **on-treatment** period is defined as the time from the first injection of the IMP up to 30 days (7 days for hypoglycemia) after the last injection of the IMP.

- The 30-week core on-treatment period is defined as the time from the first injection of IMP up to Visit 10 (Week 30) (or Day 210 if Visit 10 [Week 30] visit is missing) or up to 30 days (7 days for hypoglycemia) after the last injection of IMP, whichever comes earlier.
- The **post-treatment** period is defined as the period from the end of the whole on-treatment period.

The **on-study observation period** is defined as the time from first injection of IMP up to either the last protocol-planned visit or the date of last available information if participants discontinue the study prematurely (ie, the date collected on e-CRF page “Completion of End of Study/Follow-up”), whichever is later.

- The **30-week on study observation period** is defined as the time from first injection of IMP up to Visit 10 (Week 30) (or Day 210 if Week 30 visit 10 is missing), irrespective of whether subject had discontinued, or IMP was still being used at Week 30.

The post-study observation period is defined as the time after the end of the on-study observation period until the date of resolution/stabilization of all SAE, AESI and/or AERSM, up to database lock.

Adverse event observation period

- **Pre-treatment AEs** are AEs that developed or worsened or became serious during the pre-treatment period
- **Treatment-emergent AEs (TEAEs)** are AEs that developed or worsened or became serious during the on-treatment period
- **Post-treatment AEs** are AEs that developed or worsened or became serious during the post-treatment period

All AEs (including SAEs, AEs of special interest and AEs requiring specific monitoring) will be coded to a lower-level term (LLT), preferred term (PT), high-level term (HLT), high-level group term (HLGT), and associated primary system organ class (SOC) using the version of MedDRA currently in effect at the time of database lock.

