2.4.5.1 Analyses of adverse events

Generalities

The primary focus of AE reporting will be on TEAEs. Pretreatment and posttreatment AEs will be described separately.

If an AE date/time of onset (occurrence, worsening, or becoming serious) is incomplete, an imputation algorithm will be used to classify the AE as pretreatment, treatment-emergent, or posttreatment. The algorithm for imputing date/time of onset will be conservative and will classify an AE as treatment emergent unless there is definitive information to determine it is pretreatment or posttreatment. Details on classification of AEs with missing or partial onset dates are provided in [Section 2.5.3](#).

Incidence tables will present AEs by SOC, HLT, HLT, and PT, sorted in SOC internationally agreed order and HLT, HLT and PT sorted alphabetically for each treatment group, and the number (n) and percentage (%) of participants experiencing an AE. Multiple occurrences of the same event in the same participant will be counted only once in the tables within a treatment phase. The denominator for computation of percentages is the safety population within each treatment group.

Sorting within tables ensures the same presentation for the set of all AEs within the observation period (pretreatment, treatment-emergent, and posttreatment). For that purpose, the table of all TEAEs presented by primary SOC and PT sorted by the internationally agreed SOC order and decreasing frequency of PTs within SOCs will define the presentation order for all other tables unless otherwise specified. In case of equal frequencies of PTs within a SOC, the alphabetic order will be applied. Sorting will be based on the incidence in the efpeglenatide 6 mg group.

The internationally agreed order of SOCs shown below was described in the Introductory Guide MedDRA Version 19.1, September 2016 International Conference on Harmonisation for SOC:

1. Infections and infestations
2. Neoplasms benign and malignant (including cysts and polyps)
3. Blood and lymphatic system disorders
4. Immune system disorders
5. Endocrine disorders
6. Metabolism and nutrition disorders
7. Psychiatric disorders
8. Nervous system disorders
9. Eye disorders
10. Ear and labyrinth disorders
11. Cardiac disorders
12. Vascular disorders
13. Respiratory, thoracic, and mediastinal disorders
14. Gastrointestinal disorders
15. Hepato-biliary disorders
16. Skin and subcutaneous tissue disorders
17. Musculoskeletal, connective tissue, and bone disorders

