The number of events confirmed by adjudication, will be summarized by treatment group.

Analysis of pretreatment and posttreatment adverse events

- All pretreatment AEs by primary SOC and PT, showing the number (%) of participants with at least 1 pretreatment AE
- All posttreatment AEs by primary SOC and PT, showing the number (%) of participants with at least 1 posttreatment AE
- All pretreatment SAEs by primary SOC and PT, showing the number (%) of participants with at least 1 pretreatment SAE
- All posttreatment SAEs by primary SOC and PT, showing the number (%) of participants with at least 1 posttreatment SAE.

Analysis of adverse events during the 30-week on study observation period

The following selected AE will also be summarized for the 30-week on-study observation period as defined in [Section 2.1.4](#):

- Overview of AEs
- AEs (by primary SOC, HLGT, HLT, and PT, showing number (%) of participants with at least 1 adverse event)
- SAE (by primary SOC, HLGT, HLT, and PT, showing number (%) of participants with at least 1 serious adverse event)
- AEs leading to death.

Analysis of COVID-19 related adverse events

COVID-19 related AEs during the whole on-treatment period will be presented for the number (%) of participants with at least one event and by primary SOC and PT.

Listings

Supportive AE listings will be provided for all SAEs, AESIs/AERSM, AEs leading to death, and AEs leading to treatment discontinuation. These listings will include at least the following information, sorted by treatment, participant identification, and onset date: treatment, participant identification, country, age, gender, race, primary SOC, PT, reported term, onset date, study day (relative day to the start date of IMP), AE duration, duration of exposure, intensity, corrective treatment, action taken with IMP, relationship to IMP/NIMP/study procedures, outcome, date of death (if any), seriousness, seriousness criteria, and AE status (“Pre” for a pre-treatment AE; “T” for a TEAE; and “Post” for a post-treatment AE).

Similar to the AE listing, a listing for all adjudicated AEs will be provided with adjudication outcome.

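### Post-treatment AE percentages mix observation windows of 12 to 18 days and up to about 400 days, so arms can differ without a drug effect if stopping differs and stoppers stay in follow-up

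*Protocol*

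**What the plan says.** **Window.** Protocol section 9.4.2 ends the on-treatment period 30 days after the last injection: "The whole on-treatment period is defined as the time from the first injection of IMP up to 30 days (7 days for hypoglycemia" in the case of hypoglycemia). The next segment follows directly: "The post-treatment period is defined as the time starting 31 days (8 days for hypoglycemia) after the last injection of IMP". SAP section 2.1.4 gives it no fixed length; that "period is defined as the period from the end of the whole on-treatment period".

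**Follow-up.** The protocol synopsis plans "A 6-week Follow-up Period to collect post-treatment safety information for all participants after last dose of IMP". For those who stop IMP early, section 7.1.1 says: "Participants will be followed-up according to the study procedures specified in this protocol up to the scheduled date of study completion". Footnote a of the Schedule of Activities says the same. Section 8.3.1 collects AEs until each participant's end of study.

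**Tables.** SAP section 2.4.5.1 plans: "All posttreatment AEs by primary SOC and PT, showing the number (%) of participants with at least 1 posttreatment AE", with a matching table for SAEs. The general rule of that section is: "The denominator for computation of percentages is the safety population within each treatment group". For the post-treatment tables it plans no person-time, no restriction to participants who entered the window, and no split by completion of treatment.

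**Tables that ignore treatment status.** Protocol Table 6 adds: "Adverse events, SAEs and AEs leading to death tables also will be presented on the 30-week on-study period too". SAP section 2.4.5.1 repeats this and stops at Week 30. SAP section 2.1.4 defines an on-study period to the end of study, but over that whole period the safety section names only deaths (SAP sections 2.1.4.1 and 2.4.5.3).

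**The concern.** The percentage combines two groups with very different observation times: completers, watched for a couple of weeks, and retained early stoppers, watched for months. The mix is fixed after randomization by how many stop, when they stop, and how many stay in the study. Two arms with the same underlying AE rate can therefore show different post-treatment percentages.

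Stopping could plausibly differ by arm. Protocol section 4.3 describes nausea and vomiting as dose related, and section 7.1.1 lists confirmed intolerance among the reasons to stop IMP. A reader who compares columns could take an artefact of follow-up time for a dose trend, or dismiss a real difference as such an artefact.

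For general AEs that start after Week 30 and more than 30 days off IMP, no other comparative incidence table is planned. TEAE tables have closed by then, and the treatment-independent AE tables end at Week 30.

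**Working it through.** **1. Timeline.** The documents state no length for the post-treatment window, so the check starts from the visit schedule. Screening, treatment and follow-up sum to 3 + 56 + 6 = 65 weeks, as stated. Visit 15 is at Day 392 + 42 = Day 434 (±7), as in the Schedule of Activities.

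**2. Length of the window**
- Completer: 42 − 30 = 12 days (5 to 19 with the ±7-day visit window). If the last weekly injection is at Week 55 (Day 386) and Visit 15 is on Day 434, it is 434 − 386 − 30 = 18 days.
- Early stopper with last injection on day t, followed to Day 434: 434 − 30 − t = 404 − t. This gives 403 days for Day 1, 375 for Day 29, 319 for Day 85 and 194 for Day 210.

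**3. Expected percentages with no drug effect**

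Assumptions, none of them from the documents: a constant rate λ = 1 first AE per participant-year in every arm; stopping days uniform over Days 1 to 385; a 12-day completer window; a share r of stoppers followed to Day 434, the rest contributing no post-treatment time.

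- Chance of a post-treatment AE in a window of w days: p(w) = 1 − exp(−λw/365.25).
- Completer: p(12) = 3.2%.
- Retained stopper: mean window 404 − 193 = 211 days. Averaging p over the stopping days (not evaluating it at the mean) gives 41.3%.
- Arm percentage at stopping fraction d: (1 − d) × 3.2% + d × r × 41.3%.

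| Retained share r | 5% stop | 10% stop | 20% stop | Ratio, 20% to 10% |
|---|---|---|---|---|
| 1 | 5.1% | 7.0% | 10.8% | 1.54 |
| 0.5 | 4.1% | 5.0% | 6.7% | 1.35 |
| 0 | 3.1% | 2.9% | 2.6% | 0.89 |

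Under these assumptions the direction changes where r × 41.3% = 3.2%, that is, at about 8% retention (3.2/41.3).

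**4. Sensitivity, 10% versus 20% stopping**
- λ = 0.5, full retention: 3.9% versus 6.1% (ratio 1.58).
- λ = 2, full retention: 12.0% versus 17.6% (ratio 1.47).
- λ = 1, 18-day completer window: 8.5% versus 12.1% with full retention (ratio 1.43); ratio 1.25 with half retained and the rest contributing no time.

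**5. SAEs.** With 100 participants per arm and full retention, moving from 10% to 20% stopping turns 10 completers into stoppers. The expected excess is 10 × (stopper risk − completer risk).
- Assumed 0.05 SAEs per participant-year: 10 × (2.84% − 0.16%) ≈ 0.27 participants.
- Assumed 0.1 per participant-year: 10 × (5.57% − 0.33%) ≈ 0.5 participants.

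**6. Effect of a person-time denominator.** With full retention, 100 participants contribute 100 × (0.10 × 211 + 0.90 × 12)/365.25 = 8.7 post-treatment participant-years at 10% stopping. At 20% they contribute 100 × (0.20 × 211 + 0.80 × 12)/365.25 = 14.2. With one common AE rate both arms then have the same expected rate per participant-year, while the planned percentages differ by a factor of 1.54.

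**The case against.** **Retention decides direction and size.** A reader might infer that an arm with more discontinuation must show more post-treatment AEs. The documents do not support that. Protocol section 7.2 lets participants leave the study at any time, and the plan expects few retrieved dropouts, with a back-up imputation if any arm has fewer than 5. That expectation may reflect few stoppers rather than poor retention, but it does not support assuming full follow-up. With no stoppers retained the difference slightly reverses. This objection stands, and the point is therefore conditional.

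**No discontinuation rates are given.** A reader might infer a two-fold spread between arms, or that the higher doses will stop more often. The first needs 5% versus 20% stopping with full retention. The second goes beyond protocol section 4.3, which says GI events are dose related and generally decrease after the first injection, and describes escalation meant to limit them. Both remain assumptions.

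**Serious events have other cover.** A reader might infer that a real late signal could not be told from the artefact. For serious events that goes too far. SAP section 2.4.5.1 plans listings of SAEs, AESIs and AERSMs, and AEs leading to death or discontinuation, each with study day, duration of exposure and a pre-, on- or post-treatment flag. Adjudicated events are counted by arm with no on-treatment restriction stated. Deaths are summarized over the whole on-study period. SAP section 2.2 provides Kaplan-Meier curves for discontinuation, and SAP section 2.4.3.1 summarizes exposure and study duration. This also stands.

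**The tables are descriptive.** TEAEs are the primary focus, no systematic testing is planned, and no endpoint rests on the post-treatment percentage. This limits the importance of the point. It does not make percentages over unequal windows comparable.

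**Conclusion.** The point holds in conditional form. The denominator in SAP section 2.4.5.1 takes no account of windows of about 12 to 18 days for completers and up to about 400 days for retained early stoppers. If stopping differs by arm and an appreciable share of stoppers is retained, the post-treatment percentages differ without a drug effect.

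The window lengths follow from the documents. The AE rate, the stopping fractions and times, and the retention are assumptions, so the percentages illustrate the mechanism and do not predict this trial's results. The likely effect on SAE counts is below one participant per arm at the assumed SAE rates, and serious events are partly covered elsewhere. What remains is mainly the comparative incidence of AEs that start after Week 30 and more than 30 days off IMP, in descriptive tables. This is a cheap improvement; it does not affect the efficacy conclusions or the TEAE tables.

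**What to change.** Make two changes in SAP section 2.4.5.1.

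1. In the post-treatment AE and SAE tables, show for each arm the participant-years of post-treatment observation and the rate per 100 participant-years, separately for treatment completers and early stoppers. The split matters because the AE rate may change with time since the last dose; completers and stoppers are groups formed after randomization, so it aids interpretation and is not a randomized comparison.
2. Repeat the AE and SAE tables planned for the 30-week on-study period over the whole on-study observation period already defined in SAP section 2.1.4. Arms are then compared irrespective of IMP use to the end of follow-up.

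The SAP already uses participant-year rates for hypoglycemia (section 2.4.5.2) and product complaints (section 2.4.5.4). The data are already collected, and trial conduct and type I error are unaffected. The cost is SAP wording and a slightly larger output set.

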**Table 6 - Safety analyses**

Endpoint	Statistical Analysis Methods
AEs	
All AEs will be coded to a "LLT", "PT", "HLT", and "HLGT" and associated "SOC" using the version of MedDRA currently in use by the Sponsor at the time of database lock.
 
Adverse event incidence tables will be presented by primary SOC (sorted by internationally agreed order), HLGT, HLT and PT (sorted in alphabetical order) for each treatment group, showing the number (n) and percentage (%) of participants experiencing an AE.
 
The primary focus of AE reporting will be on TEAEs. Pretreatment and posttreatment AEs will be described separately.
 
Adverse event incidence table will be provided by treatment group for all types of TEAEs: all TEAEs, all treatment-emergent SAEs, all TEAEs leading to permanent treatment discontinuation and all TEAEs leading to death.
 
Tables will be presented on the "30-week main on-treatment period" and on the "whole on-treatment period including the 26-week controlled Treatment Extension Period".

Endpoint	Statistical Analysis Methods
	Adverse events, SAEs and AEs leading to death tables also will be presented on the 30-week on-study period too.
Hypoglycemia	
The number (%) of participants with at least 1 hypoglycemia event during the whole on-treatment period will be assessed per type of hypoglycemic event (see Section 8.2.5) and according to time of occurrence (nocturnal [ie, 00:00 to 05:59 am], any time of the day). Documented hypoglycemia (symptomatic or asymptomatic) will be also evaluated for the more stringent SMPG threshold of <54 mg/dL (3.0 mmol/L).
 
Summaries will be presented overall and by type of event for each treatment group.
 
The total number of events (per 100 participant-years) will be computed and summarized overall and by type of event for each treatment group.
 
Similar summaries will also be provided for the 30-week core on-treatment period.

Vital signs and laboratory data	For quantitative safety parameters based on central laboratory/reading measurements, descriptive statistics will be used to summarize results and change from Baseline values by visit and treatment group.
ECG & Holter data	
The incidence of potentially clinically significant abnormalities (PCSA), defined as abnormal values considered medically important by the Sponsor according to predefined criteria/thresholds based on literature review, will be summarized at any time during the 30-week core on-treatment period and during the whole on-treatment period.
 
Results will be presented both in standard international and conventional US units
 
The incidence of Normal and Abnormal ECG status at any time during on-treatment period will be summarized by treatment group whatever the Baseline level and according to Baseline status.
 
Tables will be presented on the “30-week main on-treatment period” and on the “whole on-treatment period including the 26-week controlled Treatment Extension Period”

Exploratory	Will be described in the statistical analysis plan finalized before database lock

AE adverse event; ECG electrocardiogram; HLGT higher-level grouped term; HLT higher-level term; LLT lower-level term; MedDRA Medical Dictionary for Regulatory Activities; PCSA potentially clinically significant abnormalities; PT preferred term; SAE serious adverse event; SOC system organ class; TEAE treatment-emergent adverse event.

